6.2 Screening for I/E Criteria

At the initial screening, the investigator should review the inclusion and exclusion criteria based on the information collected at the screening visit. Any change to status affecting conformance to inclusion and exclusion criteria at subsequent visits prior to randomization must be evaluated. At randomization, the investigator should confirm the run-in drug compliance.

6.3 Medical History

The following information will be collected at the screening visit:

6.3.1 General Demographics and Characteristics

1. Date of birth, age, sex, and race, and whether a female subject is of childbearing potential or not.
2. Significant medical and surgical history, including dates of diagnoses and procedures and whether the condition is ongoing, if applicable.

6.3.2 Diabetes History

1. History of all medications used to treat diabetes (to be recorded in the concomitant medication form), including start date, duration of use, and stop date, if applicable.

2. History of complications due to diabetes, including nephropathy, retinopathy, neuropathy, non-traumatic amputations, and diabetic ketoacidosis, including date of diagnosis
3. Frequency of hypoglycemic events (per week) that are symptomatic or require assistance.

6.3.3 Cardiovascular Disease History

History of cardiovascular disease including presence of angina, congestive heart failure (including New York Heart Association [NYHA] classification), known atherosclerotic cardiovascular disease, prior MI, transient ischemic attack or stroke, and prior cardiac or peripheral re-vascularization procedures. The history should include the date of diagnosis and the current status of diagnosis (resolved or ongoing).

6.3.4 Medication History

1. Use of prescribed or non-prescribed medications, including name of medication, indications for usage, start and stop dates, dose, and frequency
2. Use of supplements, including over the counter drugs, vitamins, herbal preparations, and dietary supplements within the past 30 days prior to screening. Each medication history will include the agent used, indication for usage, start and stop dates, dose, and frequency.

6.4 Diet and Exercise Counseling

Subjects will receive counseling regarding an appropriate diet and exercise regimen to aid in glycemic control based on standards of medical care in diabetes throughout the study. In addition, all subjects are encouraged to consume enough liquid to maintain adequate hydration.

6.5 Physical Examination

A complete physical examination will be performed by the investigator at the time points indicated in the Schedule of Events ([Appendix 1](#)). The examination will include measurement of body weight and height (height will be measured only at screening), general assessment of all body systems including the skin, head, eyes, ears, nose, throat, neck, heart, lungs, abdomen, lymph nodes, and extremities.

The body weight must be determined using a scale that is calibrated. The same scale should be used throughout the study duration.

6.6 Abbreviated Physical Examination

An abbreviated physical examination will include body weight and general assessment of the skin, heart, lungs and abdomen. Abbreviated physical examinations will be performed by the investigator at the time points indicated in the Schedule of Events ([Appendix 1](#)), unless clinically indicated.

The body weight must be determined using a scale that is calibrated. The same scale should be used throughout the study duration.

6.7 Vital Signs

Vital signs will be measured at the time points indicated in the Schedule of Events ([Appendix 1](#)) and will include supine, sitting and standing BP measurements, and heart rate.

Devices designed to measure BP from the finger or wrist may not be used. The left arm and same cuff sizes should be used for each measurement at all visits. If the left arm cannot be used at the screening visit or during the study for BP measurements, the reason should be documented, and the right arm should be used for BP measurements for all subsequent visits.

At each visit, BP measurements will be obtained using a calibrated sphygmomanometer while the subject is in sitting, supine, and standing positions. A single heart rate measurement should be taken just prior to the BP evaluation in the sitting, supine, and standing positions.

All readings are to be entered into the source document and CRF for all subjects. The date and time of BP measurements should be captured in the source document and CRF. BP will be assessed first in the sitting position. Sitting BP and heart rate will be measured after the subject has been sitting for at least 5 minutes with feet on the floor and arm supported at heart level.

After sitting BP measurement has been completed, supine and standing BP will be measured to evaluate orthostatic vital signs. Supine and standing blood pressure measures will not be used to determine eligibility for the study. First, the subject will lie flat for 5 minutes and have heart rate and supine blood pressure measured using the same equipment and arm as described for sitting BP. Once the supine BP measurement is complete, the subject will stand. Standing BP and heart rate will be measured after 2 minutes of standing. For standing BP measurements, the arm should be supported and extended such that the cuff is at heart level.

6.8 Electrocardiography

A 12-ECG will be conducted at the time points indicated in the Schedule of Events in [Appendix 1](#) and whenever clinically indicated. This procedure should be performed in the supine position after at least 10 min of rest. ECG parameters measured will be the RR interval, PR interval, QRS duration, and QT interval. Each ECG should also be assessed by the investigator for signs of ischemia, clinically significant hypertrophy, and clinically significant T-wave abnormalities or arrhythmia.

It is the investigator's responsibility to review the results of the ECG as they become available. For each abnormal ECG result, the investigator shall ascertain if the observation represents a clinically significant change from the screening ECG for that individual subject. This determination does not necessarily need to be made the first time an abnormal result is observed. The investigator may repeat the ECG to verify the original result. If the ECG result

is determined to be a clinically significant and abnormal change from baseline for that subject, it is considered to reflect an AE.

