PR	time from the beginning of the P wave to the beginning of the QRS complex in electrocardiogram
QRS	QRS complex is a name for the combination of three of the graphical deflections seen on a typical electrocardiogram
QT	corrected QT interval is a measure of the time between the start of the Q wave and the end of the T wave in the heart's electrical cycle
RBC	red blood cell (count)
SAE	serious adverse event
SBP	systolic blood pressure
SD	standard deviation
SGLT2	sodium glucose cotransporter 2
SMBG	self-monitored blood glucose
SOP	standard operating procedure
SU	sulfonylurea
SUSAR	serious and unexpected suspected adverse event
T2DM	type 2 diabetes mellitus

TC	total cholesterol
TEAE	treatment emergent adverse event
TG	triglycerides
TZD	thiazolidinedione
UACR	urine albumin to creatinine ratio
UADR	unexpected adverse drug reaction
UGE	urinary glucose excretion
ULN	upper limit of normal
UPT	urinary pregnancy test
UTI	urinary tract infections
WBC	white blood cell (count)
WHO-DD	World Health Organization Drug Dictionary
WOCBP	women of childbearing potential

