1. GLOSSARY OF ABBREVIATIONS

Abbreviation	Description
ADA	American Diabetes Association
AE	Adverse Event
ANCOVA	Analysis of Covariance
ATC	Anatomical Therapeutic Chemical
BMI	Body Mass index
CEC	Cardiovascular Endpoint Committee
CI	Confidence Interval
CRF	Case Report Form
CTCAE	Common Terminology Criteria for Adverse Events
CV	Coefficient of Variation
dL	Deciliter
DSMB	Data and Safety Monitoring Board
ECG	Electrocardiogram
eGFR	Estimating Glomerular Filtration Rate
FPG	Fasting Plasma Glucose
GLP-1	Glucagon-like Peptide-1
GMI	Genital Mycotic Infection
GGT	Gamma Glutamyl Transferase
HbA1c	Hemoglobin A1c
HBsAg	Hepatitis B Surface Antigen
HCV	Hepatitis C Virus
Hct	Hematocrit
HDL-C	High Density Lipoprotein Cholesterol
Hgb	Hemoglobin
HIV	human immunodeficiency virus
ICH	International Conference on Harmonization

Abbreviation	Description
ITT	Intention to Treat
IVRS	Interactive Voice Randomization System
IWRS	Interactive Web Randomization System
LDL-C	Low Density Lipoprotein Cholesterol
LOCF	Last Observation Carried Forward
MACE	Major Adverse Cardiovascular Event
Max	Maximum
MCH	Mean Cell Hemoglobin
MCHC	Mean Cell Hematocrit
MCV	Mean Cell Volume
MDRD	Modification of Diet in Renal Disease
MedDRA	Medical Dictionary for Regulatory Activities
Mg	Milligram
MI	Myocardial Infarction
Min	Minimum
mL	Milliliter
MMRM	Mixed Model Repeated Measures
MODY	Maturity-onset Diabetes of the Young
N/A	Not Applicable
NA	Not Applicable
Na	Sodium
NCI	National Cancer Institute
OHA	Oral Hypoglycemic Agent
PP	Per Protocol
PR	Time from the beginning of the P wave to the beginning of the QRS complex in electrocardiogram
PT	Preferred Term
QRS	Graphical deflections corresponding to ventricular depolarization in a typical electrocardiogram

Abbreviation	Description
QTc	Time between the start of the Q wave and the end of the T wave in the ECG, corrected for heart rate
RBC	Red Blood Cell
RR	Time between the start of one R wave and the start of the next R wave in the ECG
SAE	Serious Adverse Event
SAP	Statistical Analysis Plan
SBP	Systolic Blood Pressure
SD	Standard Deviation
SE	Standard Error
SGLT2	Sodium Glucose Linked Transporter 2
SI	Standard International System of Units
SMBG	Self-Monitored Blood Glucose
SOC	System Organ Class
SOP	Standard Operating Procedure
SS	Safety Set
T2DM	Type 2 Diabetes Mellitus
TC	Total Cholesterol
TEAE	Treatment Emergent Adverse Event
TG	Triglycerides
TLF	Table, Listing And Figure
TZD	Thiazolidinedione
UACR	Urine Albumin To Creatinine Ratio

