3.4. SAFETY OBJECTIVES

- To compare the effects of bexagliflozin vs. glimepiride on the incidence of adverse events of interest. Adverse events of interest are urinary tract infections (UTI), pyelonephritis urosepsis, genital mycotic infections (GMI), diuretic effects including hypovolemia, hypotension episodes, hypoglycemia, hepatotoxicity, major adverse cardiovascular events (MACE), fractures, malignancies, hypersensitivity reactions, acid-base disorders including diabetic ketoacidosis, rash, and renal failure events
- To compare the effects of bexagliflozin vs. glimepiride on general safety assessments including treatment emergent adverse events, clinical laboratory events, 12-lead electrocardiograms (ECG) parameters, physical examinations, vital signs including orthostatic blood pressure, and use of concomitant medications

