3.8. DETERMINATION OF SAMPLE SIZE

An approximate total of 420 subjects will be randomized and equally allocated to receive:

- bexagliflozin tablets, 20 mg and glimepiride, placebo capsules (referred to as bexagliflozin group in this document)
- bexagliflozin tablets, placebo and glimepiride capsules, 2 mg, 4 mg, or 6 mg (referred to as glimepiride group in this document).

The sample size calculation for this study is based on a two group t-test with a one-sided significance at the 0.025 level and the following assumptions:

- The non-inferiority limit (margin) for mean change from baseline to week 60 in HbA_{1c} comparing bexagliflozin group to glimepiride group will be 0.35%
- The standard deviation for the change from baseline to week 60 in HbA_{1c} for bexagliflozin group and glimepiride group will be 1.0%

Under the above assumptions, an estimated sample size of 172 subjects is needed in each treatment arm to determine non-inferiority of bexagliflozin to glimepiride with respect to change in HbA_{1c} at week 60 from baseline. This estimation is based on a one-sided t-test with 90% power at a 0.025 level of significance. A sample size of 210 per arm has been selected to account for approximate 18% drop-out rate and to allow adequate safety evaluation. The total sample size for this study will be 420 subjects.

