9.6. ELECTROCARDIOGRAM

A 12-lead electrocardiogram (ECG) will be conducted at the screening visit (Day - 11), on baseline visit (Day -3 to -5), at weeks 24, 60, and 96. ECG parameters measured will be the RR interval, PR interval, QRS duration, QT interval, and QTcB. Each ECG should also be assessed by the investigator for signs of ischemia, clinically significant hypertrophy, and clinically significant T-wave abnormalities or arrhythmia.

If a subject's ECG parameters cannot be determined due to pacemaker placement or atrial fibrillation, the ECG parameters will be considered missing. Any machine generated values such as 0 or 9999 will be excluded from the analyses.

For each abnormal ECG result, the investigator shall ascertain if the observation represents a clinically significant change from the screening ECG for that individual subject (this determination, however, does not necessarily need to be made the first time an abnormal result is observed. The investigator may repeat the ECG to verify the results of the original result). If the ECG result is determined to be a clinically significant and abnormal change from baseline for that subject, it is considered an AE.

For the ECG parameters, observed values and change from baseline from scheduled visits will be summarized with descriptive statistics by treatment group and overall at each visit. The maximum change from baseline from scheduled visits will also be provided for ECG parameters.

For the ECG overall assessment, the number and percentage of subjects in each overall assessment category (normal, abnormal but not clinically significant, abnormal and clinically significant, missing) will be presented by treatment group and overall at each visit.

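### SAP 9.6 names Bazett's QTcB as its only rate-corrected QT; pre-specifying QTcF beside it would show whether a QTc difference depends on the correction

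*Protocol*

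**What the plan says.** Protocol 6.8 collects the inputs for any rate correction and names no corrected interval: "ECG parameters measured will be the RR interval, PR interval, QRS duration, and QT interval". The choice of correction appears only in SAP 9.6: "ECG parameters measured will be the RR interval, PR interval, QRS duration, QT interval, and QTcB". The SAP does not expand QTcB. Its glossary has QTc only, described as "Time between the start of the Q wave and the end of the T wave in the ECG, corrected for heart rate", with no formula. I read QTcB in its usual sense, Bazett's QT/RR^(1/2). SAP section 13, on changes from the protocol, does not mention the correction.

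For the ECG parameters, SAP 9.6 says that "observed values and change from baseline from scheduled visits will be summarized with descriptive statistics by treatment group" at each visit, and that "The maximum change from baseline from scheduled visits will also be provided for ECG parameters". It plans no test and no QTc threshold categories. The post-baseline ECGs are at weeks 24, 60 and 96. Table 14.3.6.2 holds the parameter summaries, but its title does not list the parameters.

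The comparison between arms is a stated safety objective (SAP 3.4): "To compare the effects of bexagliflozin vs. glimepiride on general safety assessments including treatment emergent adverse events, clinical laboratory events, 12-lead electrocardiograms (ECG) parameters".

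There is also a small mismatch of terms. The protocol's abbreviation list explains QT with the words "corrected QT interval is a measure of the time between the start of the Q wave and the end of the T wave", whereas section 6.8 lists QT with no correction.

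**The concern.** A rate correction should leave a quantity that does not move when only heart rate moves. Bazett's does so only if QT is proportional to the square root of RR. If the true exponent is smaller, it over-corrects: the faster-beating arm, or a subject at a faster visit, shows a longer QTcB with no change in repolarisation. A rate shift in the other direction could offset a real QTc change.

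The documents name features that might move heart rate differently in the two arms. Diuretic effects, hypovolemia and hypotension are events of interest. Protocol 3.2.3 reports lower blood pressure in an earlier bexagliflozin study, and says that sulfonylureas raise the risk of hypoglycemia. With one correction planned, a QTcB difference could not be separated from a rate effect within the QTc summaries themselves. Choosing a second correction after seeing the data would be post hoc.

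**Working it through.** **Inputs.** Neither document gives a QT value, a heart rate, a QT–RR exponent or an expected heart-rate effect, so there is no figure of the plan's to reproduce. I assume QT = 400 ms × RR^b with RR = 60/HR in seconds, a resting rate of 70 or 75 bpm, and b from 0.30 to 0.50. There is no true QTc effect in any row.

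**Formulas.**
- QTcB = QT/RR^(1/2) = 400 × (60/HR)^(b − 1/2)
- QTcF = QT/RR^(1/3) = 400 × (60/HR)^(b − 1/3)

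**One case in full.** Take b = 0.30. At 70 bpm, QTcB = 400 × 0.8571^(−0.20) = 412.52 ms. At 73 bpm, QTcB = 400 × 0.8219^(−0.20) = 416.00 ms. A 3 bpm difference therefore gives +3.48 ms.

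**Shift in ms for the faster arm** (starting rate 70 / 75 bpm):

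| b | QTcB, +1 bpm | QTcB, +3 bpm | QTcF, +1 bpm | QTcF, +3 bpm |
|---|---|---|---|---|
| 0.30 | 1.17 / 1.11 | 3.48 / 3.29 | 0.19 / 0.18 | 0.56 / 0.53 |
| 1/3 | 0.97 / 0.92 | 2.88 / 2.72 | 0 / 0 | 0 / 0 |
| 0.40 | 0.58 / 0.54 | 1.71 / 1.61 | −0.37 / −0.35 | −1.11 / −1.03 |
| 0.417 | 0.48 / 0.45 | 1.42 / 1.33 | −0.47 / −0.43 | −1.38 / −1.28 |
| 0.50 | 0 / 0 | 0 / 0 | −0.92 / −0.85 | −2.72 / −2.51 |

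**Break-even.** The residual exponents are b − 1/2 and b − 1/3. They are equal in size midway, at b = (1/2 + 1/3)/2 = 0.417. Below that QTcF has the smaller error, and above it QTcB does.

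**What the pair shows.** QTcB minus QTcF moves by 0.85 to 0.98 ms per bpm in every row (for example 1.17 − 0.19 = 0.98). A rate difference therefore appears as disagreement between the two corrections, whatever b is.

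**Maximum change.** For one subject whose rate rises from 70 to 80 bpm, QTcB moves by +5.5 ms (b = 0.40) to +11.2 ms (b = 0.30), and QTcF by −3.5 to +1.8 ms. At b = 0.50 the shifts are 0 and −8.6 ms. Equal rate variability in both arms would affect the maximum in both, and would not by itself create a between-arm difference.

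**Scale against noise.** The SAP gives "A sample size of 210 per arm has been selected to account for approximate 18% drop-out rate", from a requirement of 172. With an assumed SD of QTc change of 15–25 ms, the 95% half-width for a difference in means, 1.96 × SD × √(2/n), runs from 1.96 × 15 × √(2/210) = 2.9 ms to 1.96 × 25 × √(2/172) = 5.3 ms. An artefact of 1–2 ms lies inside that. Only the larger rate differences would be visible.

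**The case against.** The strongest objection is that the preference for QTcF rests on an exponent that the documents do not give. At b = 0.5 Bazett is exact and QTcF is the biased one. This stands: a reader might infer that QTcF should replace QTcB, and the documents do not support that. They support only showing both.

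A reader might also infer that the arms' heart rates will differ and that the difference will appear as QTc prolongation. The documents neither predict nor exclude a difference. If volume effects raised the rate in one arm and hypoglycemia raised it in the other, the two would partly cancel between arms. ECGs are taken supine after at least 10 minutes of rest. Subjects are to hold that day's bexagliflozin until after the blood draw and glimepiride until the first meal, and the visit lists put the ECG ahead of the draw. The change summaries use scheduled visits only, so ECGs prompted by an acute event do not enter them. This stands as well, and it is why the point is conditional.

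Third, RR and uncorrected QT are summarised beside QTcB, pulse rate is summarised under SAP 9.5, and the investigator judges clinically significant ECG changes as adverse events whatever the correction. No hypothesis test depends on QTcB, and QT prolongation is not among the events of special interest. For mean changes this largely answers the concern, since a rate shift would be seen. It does not answer it for maximum change: a subject's largest changes in QT, RR and QTcB may fall at different visits, so separate summaries cannot be combined into a rate-adjusted maximum.

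Finally, the table shells and appendix are attachments outside the available text, so another correction may be specified there.

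**Conclusion.** The point holds in conditional form and is minor. It belongs to SAP 9.6; Protocol 6.8 is not at fault for listing the raw intervals. QTcB is the only rate-corrected QT named in the available text. Its mean-change and maximum-change summaries will carry a rate artefact if two things are both true: heart rate differs between arms or changes within subjects, and b is not 0.5. On the assumptions of 400 ms and 70–75 bpm, the size is about 0.5–1.2 ms per bpm for b = 0.30–0.40, falling to zero at b = 0.5.

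The documents do not show that such an artefact will occur, that Bazett is wrong for this population, or that a real QT change would go unseen. With a descriptive analysis and RR alongside, the effect on conclusions is small. What is missing is a planned way to tell whether a QTc difference, especially in maximum change, depends on the correction chosen.

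**What to change.** In SAP 9.6 and Table 14.3.6.2, pre-specify before unblinding QTcF = QT/RR^(1/3), derived from the recorded QT and RR. Report its observed values, change from baseline and maximum change by arm alongside QTcB. Write out both formulas. State that a between-arm QTc difference will be read as real only if it does not depend on the correction, and that disagreement between the two will be read together with the RR summary. If the table shells already contain a second correction, name it in SAP 9.6.

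At the same time, reconcile the protocol's abbreviation entry for QT with section 6.8.

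The cost is one derived variable and extra rows in one table. No new data, visits or procedures are needed.

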6.9 Clinical Laboratory Tests

6.9.1 Laboratory Parameters

Clinical laboratory tests are listed in [Table 3](#).

6.9.2 Sample Collection, Storage, and Shipping

6.9.2.1 Hematology, Blood Chemistry, Serum Lipids, and Glycemic Control Assessments

Blood samples for hematology, chemistry, serum lipids and glycemic control assessments will be collected. Subjects will be in a seated or supine position during blood collection. Samples will be collected at the time points indicated in the schedule of events in [Appendix 1](#) and [Appendix 2](#).

The study staff will contact each subject prior to a scheduled clinic visit to confirm the time of the visit and to remind the subject of proper fasting practice. A subject must be queried to assess compliance with an approximately 10 h fast prior to blood draw to ensure the FPG and triglycerides values can be accurately determined. If a subject has not fasted for approximately 10 h, the subject must return as soon as can be arranged (within 1 week) to provide a specimen after proper fasting.

Low-density lipoprotein-cholesterol (LDL-C) will be calculated by the Friedewald equation. If triglycerides are > 400 mg/dL, the calculated LDL-C value is invalid by this equation and will be set as missing. Direct LDL-C will be determined in subjects whose triglycerides are > 350 mg/dL at screening visit. All subsequent LDL-C of these subjects will be determined by the same direct LDL-C measurements only.

